1. BACKGROUND AND RATIONALE

Diabetes has become a worldwide pandemic affecting over 387 million individuals, including 29 million people in the United States alone. It is estimated that 15 to 25 percent of diabetic patients are expected to develop a diabetic foot ulcer (DFU) during their lifetime. As the DFU becomes intractable, the patient's quality of life and productivity are considerably affected.

The longer that a wound remains non-healed, there is an increased risk for infection, leading to amputation or even possible death. It is estimated that over 245 billion dollars are spent in total medical cost and lost wages related to the disease. The cost per episode of care can exceed \$38,000, and associated with hospitalization, ulcer recurrence, amputations, home health care and dressing changes, decrease work productivity and premature disability, feelings of social isolation and depression. In a study of Veterans with diabetes and foot ulcer, there was a 2.39 increased relative risk of death compared to those without a foot ulcer. With the estimated cost per episode of care of \$38,000, this remains a costly and important problem of particular relevance to the VA. In fact, in the VA health system alone, diabetic care takes 4% of the overall budget and 28% of the pharmacy budget with one and a half billion spent annually on diabetic Veterans.

Despite adhering to the standard wound care regimens, a major challenge faced by wound care specialists is to achieve successful treatment of these wounds. Research has shown that after 20 weeks of good wound care, only 31% of DFU heal. More recent therapeutic approaches to wound healing, such as bioengineered tissues and biologically active growth factors are very costly and have only shown modest clinical efficacy. It is important to recognize that the VA health system may not be able to justify additional financial burden of these costly new therapies. Therefore, the drive to heal DFU to prevent further complications and high costs associated with treatment is critical; as such, we are investigating, using a safe, inexpensive, well-characterized, easy to use drug that could be implemented system wide to enhance DFU repair and that may have far-reaching consequences.

Of the several identified classes of adrenergic receptors (α and β , and their subtypes), it is of particular interest to note that the major cell types of the skin--human keratinocytes, melanocytes and dermal fibroblasts express primarily β -2 adrenergic receptors (β ARs). Keratinocytes also have the capacity to synthesize the catecholamines epinephrine and norepinephrine, in essence creating a self-contained, catecholamine signaling network. The functional role of this network has been elusive. Our work suggests that it contributes to the control of cell migration, and thus to skin wound healing. When skin is wounded, repair mechanisms are activated to restore skin integrity as quickly as possible. The repair process involves the orchestration of interactions between cellular components, growth factors, chemokines, extracellular matrix proteins, which

regulate the migration and proliferation of the keratinocytes into the wound. This directional migration of keratinocyte into the wound is critical for repair and reestablishment of epithelial coherence. Our work and that of others has established that stress catecholamines such as epinephrine and norepinephrine, the natural ligands for the β AR that are present within the wound environment, impair pro-reparative functions of keratinocytes, fibroblasts, mesenchymal stem cells, and endothelial cells.

Importantly, and specifically relevant to this proposal, we have shown that blockade of the β AR with antagonists improves healing in vitro, and in animal models. Work by other investigators also supports the hypothesis that β AR antagonists can improve DFU healing. Collagen synthesis (in a pulmonary injury model) is increased by β AR antagonists. More specifically, studies have demonstrated that the topical application of β AR antagonists to wounds in diabetic rats improves not only rate of healing, but also wound vascularity. Since impairment of angiogenesis is a critical obstacle in DFU healing, the data that demonstrate that β AR antagonists improve endothelial cell migration, new vessel outgrowth from rat aortic rings, and in the classic angiogenesis assay of the chicken chorioallantoic membrane, as well as in increasing vascularity in murine skin wounds, lend particular significance to the proposed study. Indeed, a patent application for use of β AR antagonist for healing of DFU has already been filed by other investigators, albeit with no human clinical data. Additionally, there are published reports of timolol improving the epidermal barrier function in skin. Since a deficient barrier inevitably compromises the functional property of the repaired skin, one of our secondary hypotheses is that timolol restores the barrier and thus may result in a more durable healed ulcer. We will monitor transepidermal water loss (TEWL), an indicator of epidermal barrier function, using a non-invasive handheld pen-like device (Vapometer), and a secondary outcome will be the change in TEWL in timolol treated vs control treated wounds.

Our goal with the currently proposed clinical trial is to generate these unequivocal data, and to demonstrate the efficacy of this approach to improve healing in human chronic DFU.

2. OBJECTIVES

The primary objective of this study is to assess the effectiveness of the topically applied Timoptic-XE® or timolol (a non-selective beta adrenergic receptor antagonist) versus standard of care for the treatment of non-healing diabetic foot ulcers. The primary endpoint will be the measurement of the complete ulcer closure (as defined by “skin re-epithelialization without drainage or dressing requirements) at 12 weeks. The secondary outcomes will be the following: comparison of percent difference change in size from the randomization visit to the endpoint visit (post 12 weeks) between the treatment and control group, the time to wound closure between the two groups, and wound healing rates with impact of wound size between the treatment groups and measure quality of life using VR-36 Health Survey and the Lower Extremity Functional Scale Outcome Questionnaire.

The secondary objective of study is to profile the safety of topically applied Timoptic-XE® in the treatment of DFU. We will monitor serum levels of timolol post-application to determine the plasma concentration of timolol in relation to its systemic bioavailability. Timolol levels will be determined using reversed-phase ultraperformance liquid chromatography and UV detection.

Safety endpoint will be the measurement of all the adverse events associated with the use of Timoptic-XE®.

A tertiary/ancillary objective of the study is to compare efficacy of both arms of this study, Group A (SOC + Timoptic XE) and Group B (SOC + non-biologically active gel), to a “**Real-world cohort**” – patients who are not randomized and continue to receive care for their diabetic foot ulcer(s) not within the context of this research study. Passive follow-up these screen-failed patients via CPRS will be limited to charts related to the care of their foot ulcer(s).

3. STUDY POPULATION

The study population includes all Veterans’ age 18 or older, with a documented diagnosis of diabetes and a foot ulceration that has existed for at least 4 weeks at the time of enrollment into the study. Diabetic patients with foot ulcers will be selected from a random sample of patients from the Multispecialty Wound Healing Clinic at Sacramento VA Medical Center, and the six clinical sites at the VANCHCS. In fact, there were over 15,146 patients with diabetes mellitus receiving care at the VANCHCS, which includes Sacramento VA Medical Center and 6 other satellite clinics, and approximately 1002 patients with DFU were receiving care at the VANCHCS, within the last 2 fiscal years.

[figure not shown]
Figure 2 illustrates the selection process with the anticipated number of participants in the study. With a minimum of 60% participation, there should be adequate recruitment for this study. The sites will accrue a total target sample of approximately 138 subjects and assuming approximately 35% dropout rate, the goal is to enroll 48 subjects in total, 24 subjects in each arm.

[figure not shown]
Selection of Cases and Controls:

The investigators will query the CPRS/VISTA database at the 7 respective sites of the VANCHCS. Eligible subjects will be called by the research coordinator and invited to participate in the study.

Those who agree will be given an appointment for screening and enrollment. A subject must meet all the following criteria to be eligible for study inclusion.

Figure 2: Summary of Selection Process

Board (IRB). We will perform simple allocation of the subjects using an electronic randomization for treatment assignment-since our target enrollment population is fairly homogenous.

Run-in phase (screening phase) in which all potential subjects are given the standard of therapy for 2 weeks, will be performed to determine compliance with return visits and performing standard of care dressings.

Each subject will be given a unique identifier that will have no personal information linked after assignment of a randomly computer-generated list of three repeated numbers which will be available. The request for assignment will be emailed to the Data Coordinator with a completed eligibility form, and no personal identifiers except for initials and a last 4 digits of social security. The Data Manager will assign a number and the next sequential group assignment with each subsequent request will be placed in sealed envelopes. These sealed envelopes will be provided to the pharmacist will dispense the Timoptic-XE® or non-biologically active gel hydrogel for the patients according to the arm to which they have been randomized. Subject demographics will not be provided until this assignment is complete. Participants will be randomly placed into Group A (SOC plus Timoptic-XE®) or Group B (SOC plus non-biologically active gel). There will be an estimated of 24 patients in each group. The patients will not be informed of treatment administered.

Withdrawal:

The subjects may withdraw from the study at any time during the study, upon request. The investigator may also discontinue a subject if it is determined that the subject has not responded to therapy or adverse event occurred, which requires alternative therapy, or the patient displays non-compliance with study schedule. Those subjects that have undergone treatment will be followed and documented until end of the study. If there is more than 10 percent loss to follow-up, then investigators will attempt to recruit additional subjects.

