PROTOCOL SUMMARY

TITLE OF THE STUDY: MERIT: Beta Adrenergic Antagonist For The Healing of Chronic Diabetic Foot Ulcers

Start Date: 04/01/2017
Ending Date 12/31/2024

PHASE: 2

METHODOLOGY: It is a prospective, randomized, double blinded, controlled, and parallel-group study with 2 arms. Follow up cohort will include a real-world group.

STUDY DURATION: 31 weeks

TREATMENT PHASE: 12 weeks

FOLLOW-UP PHASE: 16 weeks

REAL-WORLD GROUP: 12 weeks

STUDY CENTERS: One centralized study location Multispecialty Wound Healing Clinic at Sacramento VA Medical Center.

Note: Primary Care, Vascular, Podiatry and Dermatology clinics from the at the Veteran Affairs Northern California Health Care System (VANCHS) satellite clinics (Redding, Chico, Martinez, Oakland, McClellan, and Fairfield) will refer patients to the study location.

NUMBER OF SUBJECTS: 2 treatment arms, 24 subjects per arm for a total of 48; Screen-failed patients to be followed passively on the status of their diabetic foot ulcer via CPRS. Additional patients will be screened and enrolled for exploratory follow up to study inflammatory markers in non-healing patients.

STUDY OBJECTIVES: The primary objective of this study is to assess the effectiveness of the topically applied Timoptic-XE® or timolol (a non-selective beta adrenergic receptor antagonist (β BAR)) versus standard of care for the treatment of non-healing diabetic foot ulcers. The primary endpoint will be the measurement of the complete ulcer closure (as defined by “skin re-epithelialization without drainage or dressing requirements) at 12 weeks. The secondary outcomes will be the following: comparison of percent difference change in size from the randomization visit to the endpoint visit (post 12 weeks) between the treatment and control group, the time to wound closure between the two groups, and wound healing rates with impact of wound size between the treatment groups, change in trans-epidermal water loss measurements at sites of healed wounds, measurement of quality of life using Veterans Rand (VR-36) Health Survey, measurement of the Lower Extremity Functional Scale Outcome and the Charlson Comorbidity Index.

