- Number of incident subjects with infection, osteomyelitis and acute Charcot during the study, will be withdrawn from the study.
- Number of incidences of adverse effects will be reported from all sites and will be withdrawn from the study.
- VR-36 Health Survey, and the Lower Extremity Functional Scale Outcome Questionnaire (self-administered questionnaires) will be used to measure quality of life and provided at beginning of the study and at the study endpoint.
- Rate of transepidermal water loss will be measured weekly subsequent to wound closure and compared in the two groups.

Sample Size Estimation:

From previous studies, we expect that about 20% of the study subjects will heal in the control arm of our study by the 12th week of care. We estimate that the experimental treatment will improve this outcome with 63% of the study subjects healing by the 12th week of care (a healing rate close to that reported in the most recent case series of topical use of timolol on chronic wounds).

We will perform simple allocation of the subjects using an electronic randomization for treatment assignment-since our target enrollment population is fairly homogenous.

The sample size calculation will require the enrollment of 48 subjects (24 subjects in each arm) to provide a power of 80% to detect a difference of 43% (= 63% - 20%) in the rate of ulcer healing between the two arms by using two-sided Fisher's exact test at a significance level of 5%. It is estimated that the overall attrition will be 35%. Specifically, 10% of the subjects who are enrolled will be exited from the study prior to randomization, 10% will not meet the primary endpoint analysis inclusion requirement and 15% will not complete the study due to other factors such as treatment failure, loss to follow-up, adverse events, clinical/safety issues, and/or non-compliance. We will track the various reasons for study exit. Therefore, 138 subjects (69 subjects in each arm) will be recruited into the study after taking into account the overall attrition of 35%.

The consulting statistician will review implementation and compare major baseline demographic and prognostic characteristics to ascertain that randomization was successful. The power analysis was formulated using the STPLAN Version 4.5 (2010) with the input of the study consultant biostatistician.

Analyses:

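### The 80% power needs 24 analysed subjects per arm, but the plan also uses 24 per arm for the groups randomised and 48 for enrolment, beside a conflicting 69 per arm

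*Combined protocol and SAP*

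**What the plan says.** The combined protocol and SAP gives the trial size in three places.

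- **Protocol Summary, Number of Subjects:** "2 treatment arms, 24 subjects per arm for a total of 48".
- **Section 3, Study Population:** about 138 subjects are accrued, about 35% drop out, and the enrolment goal is 48. The randomisation paragraph then describes random placement into Group A or B and adds "There will be an estimated of 24 patients in each group". Under Withdrawal, the investigators will try to recruit more subjects if loss to follow-up passes 10%; no number is given.
- **Section 6, Sample Size Estimation:** "The sample size calculation will require the enrollment of 48 subjects (24 subjects in each arm) to provide a power of 80" per cent, "by using two-sided Fisher's exact test at a significance level of 5" per cent. The rates are 20% in the control arm and 63% on timolol. Overall attrition is put at 35%: 10% of enrolled subjects leave before randomisation, "10% will not meet the primary endpoint analysis inclusion requirement and 15% will not complete the study due to other factors". The paragraph ends with 138 subjects, 69 in each arm, to be recruited to allow for the 35%.

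The plan does not say how a randomised subject without a primary outcome enters the Fisher test.

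**The concern.** Section 6 introduces 24 per arm as the number that gives 80% power, and only afterwards allows for losses. In that calculation 24 is the number that must reach the analysis. The Protocol Summary and the randomisation paragraph of Section 3 use the same 24 as the group size, and Section 6 itself speaks of enrolling 48 while expecting a tenth of those enrolled to leave before randomisation. So 48 serves as the number enrolled, the number randomised and the number on which power is computed, although the plan expects losses between each stage.

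A team working from the Protocol Summary could end randomisation at 48, believing that the chance of missing the assumed effect is 20%. With 25% to 28% lost after randomisation, that chance would be roughly 29% to 43%, and a null result could be given more weight than it deserves. A team working from 69 per arm would run a much larger trial than the calculation calls for.

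**Working it through.** **Inputs (Section 6).** Closure 0.20 v 0.63; two-sided Fisher exact test at 5%; 24 per arm; losses of 10% before randomisation, then 10% and 15%.

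**Method.** Exact power is the sum, over all pairs of closure counts (x, y) whose two-sided Fisher p is at most 0.05, of Bin(x; n1, 0.20) x Bin(y; n2, 0.63).

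**1. The plan's own figure.** 24 per arm gives 82.5% and 23 per arm gives 79.5%. So 24 is the number needed for 80%, with no room for losses.

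**2. The inflation.** Allowing for 35% attrition:
- 24 / 0.65 = 36.9, so 37 per arm, 74 in total.
- 24 / 0.35 = 68.6, so 69 per arm, 138 in total. The printed 138 matches division by the loss fraction instead of the retained fraction.
- Check: 138 x 0.65 = 89.7, not 48, whereas 138 x 0.35 = 48.3.

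**3. Loss after randomisation.** If the 10% and 15% are shares of those randomised, the loss is 25%. If they are shares of those enrolled, it is 0.25 / 0.90 = 27.8%. With 48 randomised, 48 x 0.75 = 36 or 48 x 0.722 = 34.7 are analysed.

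**4. Power if randomisation ends at 24 per arm.** The completer column averages over independent random losses from 24 per arm. The last column keeps n at 24 and multiplies both rates by the retained fraction.

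| Lost after randomisation | Completers | Losses counted as not closed |
|---|---|---|
| 15% | 75.9% | 69.1% (0.536 v 0.170) |
| 25% | 70.9% | 59.6% (0.473 v 0.150) |
| 27.8% | 68.7% | 56.9% (0.455 v 0.144) |

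Fisher power is not smooth in n, so the exact split matters:
- 17/17: 63.6%
- 18/18: 68.8%
- 17 control, 18 timolol: 71.6%
- 18 control, 17 timolol: 73.7%
- For the 15% row, 20/20: 71.6%

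**5. Power if 69 per arm enter.** 69 x 0.65 = 44.85. At 44 per arm, power is 98.1%.

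**6. Randomised numbers that leave 24 analysed per arm.** 24 / 0.75 = 32 per arm (64 in total), or 24 / 0.722 = 33.2, so 34 per arm (68 in total). If losses count as not closed, 80% power needs 36 per arm at 25% loss (80.1%) or 38 per arm at 27.8% loss (80.8%).

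**The case against.** A reader might infer that the trial as planned has only 57% to 69% power. The documents do not support that.

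- **The plan does allow for attrition.** Section 6 raises the number to 69 per arm, and Section 3 presents 48 as what remains from 138. On that reading 48 is the number left for analysis and power is not short. This stands as a reading, but it does not repair the plan: 35% attrition from 138 leaves about 90, and 69 per arm contradicts 24 per arm.
- **Nothing caps randomisation at 48.** The 24 in Section 3 is called an estimate, and there is a clause for further recruitment. This stands too: stopping at 48 is one way to follow the text, not an instruction in it. The clause is limited, however. It is triggered only by loss to follow-up, promises only an attempt, and gives no number. With losses of just 10%, power from 24 per arm is already 78.5% for completers, or 73.8% with losses counted as not closed.
- **A 25% to 28% loss to the primary test is an assumption.** The 15% is non-completion of a study that runs to Week 31, while the primary endpoint is at Week 14, so some of these subjects will have a primary outcome. The 15% also names treatment failure, and such subjects may already be among those assumed not to close; scaling both rates down could count them twice. Section 3 also says that treated subjects are followed to the end of the study. These points make 57% a pessimistic bound. They do not restore 80%: with only 15% lacking an outcome, power from 24 per arm is about 72% to 76% for completers, or 69% with losses counted as not closed.

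**Conclusion.** The sample-size text is wrong as written. The 80% is correct for 24 analysed per arm. The plan applies the same 24 to the randomised groups, calls 48 the number enrolled, and elsewhere gives 69 per arm, a figure that does not follow from 35% attrition.

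The effect on power depends on which number governs. If randomisation ends at 24 per arm with 25% to 28% lost, power is about 69% to 71% for completers (64% to 74% across near-equal splits of about 35 analysed), and about 57% to 60% with losses counted as not closed. If 69 per arm enter and 35% are lost, it is about 98%. A low power cannot be asserted of the plan as a whole.

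The figures assume the plan's closure rates and, for the losses, that they are equal in the two arms and unrelated to closure. The 25% to 28% cases further assume that the 10% analysis exclusion and all of the 15% fall after randomisation and leave no primary outcome.

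**What to change.** In the Protocol Summary, both places in Section 3, and Section 6, state one number enrolled, one randomised and one analysed, with the power for the number analysed. Correct or remove 138 and 69 per arm in the same edit; otherwise a restated power would sit beside a recruitment figure that contradicts it. State also how a subject without a primary outcome is counted in the Fisher test.

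- **If 48 is the number randomised:** replace 80% with the lower figure that matches the chosen loss rate and the chosen handling of losses. No extra patients are needed.
- **If 48 is the number analysed:** say so, and print about 64 to 68 randomised and about 74 enrolled (48 / 0.65 = 73.8). If losses are to count as not closed, the number randomised for 80% power is instead about 72 to 76 (36 to 38 per arm).

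The first option changes wording only; its cost is a less favourable stated power. The second keeps the 80%, but commits the trial to randomising more than 48.

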4. STUDY PROCEDURES

4.1 DESIGN AND METHODOLOGY

We propose a prospective, randomized, double blinded, controlled, and parallel-group study with 2 arms to assess the effectiveness of the topically applied Timoptic-XE® or timolol (a non-selective beta-adrenergic receptor antagonist) versus standard of care for the treatment of non-healing DFU in the VA system.

4.2 DESCRIPTION OF STUDY GROUPS

Standard of care will consist of the typical foot evaluation and care provided by the Department of Veteran Affairs facilities, which will include: weekly ulcer assessment/progress and area measurement by digital photography before and after sharp debridement of ulcer, maintenance of a clean, moist ulcer environment with a non-biologically active gel (hydrogel) the use of an offloading device that protects the wound from pressure or trauma related to ambulation and other acts of daily living (such as orthotics, contact casts, crutches, wheelchairs), and infection management, if indicated.

The investigator will document the standard of care provided during clinic visits including weekly follow-up evaluations. Given the nature and complexities associated with DFU, the offloading device provided will be dependent on the subjects' ability to tolerate the specific offloading device. Adherence to offloading device will be evaluated by the investigator at each visit by observing plantar wear patterns and inquiring from the patient if offloading was used consistently as instructed. Alternative to total contact cast or instant total contact cast (camwalker), offloading devices will be offered including, but not limited to the use of felt/foam adhesive/post op shoe, custom offloading insole, and customized healing shoe in combination with gait assistive device such as a roll-a-bout scooter, walker, wheelchair or motorized scooter.

Group A: SOC plus Timoptic-XE®

Patients in the timolol group will undergo the same wound care and offloading modality as the SOC group, with weekly wound evaluation dressing changes, moist sterile gauze, dry gauze dressings.

The dosage used in this study will be 3 drops/3cm²/day that is equivalent to 0.75mg/3cm²/day.

Group B: SOC plus non-biologically active gel (hydrogel)

The placebo medication will be applied to the wound daily with the same dosage as above.

“Group” C: Passive follow up of screen-failed patients ***Does not change total # of patient enrollment

Patients that are not randomized into group A or B (i.e. meet exclusion criteria, do not meet all inclusion criteria, non-compliance, withdrawal) will be passively followed via CPRS on the status of their diabetic foot ulcers.

Drug management and record keeping

The research pharmacist will receive and manage both the non-biologically active gel (placebo) and the Timoptic-XE®. The pharmacist will compound and dispense the Timoptic-XE® or non-biologically active gel hydrogel for the patients according to the arm to which they have been randomized. She will repackage the medications into identical dispensers with a coded label and will dispense a 12-week supply to each patient according to their individual randomized unique identifier to ensure accurate storage and dispensing records. The un-blinded research pharmacist will keep record of the drug and patient treatment group assignment. Please see the VA Research Pharmacist's letter of agreement to participate as described. For Timoptic-XE® the recommended ocular dosage is 0.25mg/day (1 drop in each eye once a day). The average exposed ocular surface is about 3 cm². Based on the studies using timolol topically for ulcerative hemangiomas and the numerous case studies of topical timolol on chronic wounds, the dosage used in this study will be 3 drops/3cm²/day that is equivalent to 0.75mg/3cm²/day. Depending on

the size of the wound, the research pharmacist will dispense one or two bottles (with either Timoptic-XE® or placebo) for the 12 weeks supply as described in the table below.

Wound size (cm ²)	Number of drops	Timolol dosage (mg/day)	Timolol dosage (mL/day)	Dosage for 12-week supply (ml)	Number of bottles (timolol or placebo) dispensed to patient for 12-week supply (1 bottle = 5ml)
			Note: 1 drop = 0.05 ml		
< 0.5	1	0.25	0.05	4.2	1
> 0.5 - 0.9	1	0.25	0.05	4.2	1
> 1.0 - 1.9	1	0.25	0.05	4.2	1
> 2.0 - 2.9	2	0.5	0.1	8.4	2
> 3.0	3	0.75	0.15	12.6	3

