The secondary objective of study is to profile the safety of topically applied Timoptic- XE® in the treatment of DFU. We will monitor serum levels of timolol post-application to determine the plasma concentration of timolol in relation to its systemic bioavailability. Timolol levels will be determined using reversed-phase ultraperformance liquid chromatography and UV detection. The primary safety outcome will be the measurement of timolol serum during the treatment phase.

The secondary safety outcomes will be the following: the mean changes from baseline in systolic and diastolic blood pressure in mmHg, the mean changes from baseline in heart rate in beats per minute, and the measurement of all the adverse events associated with the use of Timoptic-XE®.

INCLUSION CRITERIA:

1. Male or female subject of any race 18 years old or older
2. Lower extremity ulcer located anywhere on the foot up to the ankle:
 - a. Of more than 30 days duration and less than 2 years duration (medically documented)
 - b. Surface area between 0.5cm² and 20cm² (as measured with the Silhouette imaging system at randomization). The ulcer with largest surface area meeting inclusion criteria will be selected as index ulcer
 - c. If two ulcers present with the same surface area, the ulcer of the longest duration will be selected as index ulcer
3. Documented Ankle Brachial Index (ABI) between 0.8 and 1.2 on the study limb or toe pressure over 65mmHg within 3 months of screening phase
4. Documented biopsy report to rule out malignancy of ulcer of > 6 months duration

EXCLUSION CRITERIA*:

A subject will be excluded from the study if any of the following criteria are met:

1. Ulcer of non-diabetic etiology, such as venous, arterial and burn wounds
2. Index ulcer is less than 3 cm in distance from any other ulcer on the same extremity
3. There are greater than 3 ulcers on the study foot
4. Index ulcer presents with any of the following: cellulitis, osteomyelitis, exposed bone, tendon or fascia, purulent exudate or gangrene
5. Index ulcer shows evidence of infection (defined as a moderate or severe rating of all of the following clinical signs/symptoms: 1) increased warmth, 2) increased pain, 3) erythema, and 4) malodorous exudate at Screening or at Randomization (Visit 1), OR total organism count > 1 x 10⁵ colony forming units (CFU) from the screening visit study ulcer culture sample)

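### The dose is stated per area with no maximum, but the dispensing table gives a flat 3 drops above 3.0 cm², and the bottle count in the text contradicts the table

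*Combined protocol and SAP*

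**What the plan says.** The dose appears twice in Section 4.2, under Group A and again under Drug management and record keeping, both times as an amount per area: "the dosage used in this study will be 3 drops/3cm²/day that is equivalent to 0.75mg/3cm²/day". Neither place gives an upper limit. For Group B: "The placebo medication will be applied to the wound daily with the same dosage as above".

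The dispensing table follows. Its columns run from wound size to drops, mg/day, ml/day, 12-week volume and bottles, the last headed "Number of bottles (timolol or placebo) dispensed to patient for 12-week supply (1 bottle = 5ml". The size bands are < 0.5, > 0.5 - 0.9, > 1.0 - 1.9, > 2.0 - 2.9 and > 3.0 cm². The last band has no upper end and carries 3 drops, 0.75 mg/day, 12.6 ml and 3 bottles. The sentence leading into the table says that, depending on wound size, "the research pharmacist will dispense one or two bottles". Earlier in the same paragraph the pharmacist "will dispense a 12-week supply to each patient".

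The Protocol Summary, inclusion criterion 2b, admits ulcers with "Surface area between 0.5cm² and 20cm²".

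**The concern.** For a 3 cm² ulcer the sentence and the table's 3-drop row agree. Most of the eligible size range lies above that, where the sentence scales the dose with area and the table does not. A pharmacist or clinician following one departs from the other.

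Four things are at stake:

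- **The tested regimen.** For larger ulcers a result could not be tied to one dose per area.
- **Safety interpretation.** Timolol serum level is the primary safety outcome, and Section 4.3.3 expects levels no higher than with ocular use. The plan does not say which reading of the dose that expectation assumes.
- **Secondary analyses.** Section 6 relates healing to wound size and to serum timolol. Under the table, dose per area falls as area rises above 3 cm², so size and dose per area are entangled.
- **Supply.** The 12-week supply cannot be covered by the bottle count in the text for anyone in the top row.

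The handout in Appendix 4 does not settle the matter. It tells patients to use the number of drops their doctor gives them and does not point to the table.

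**Working it through.** **Inputs.** From Section 4.2: 3 drops per 3 cm² (1 drop/cm²); 0.75 mg per 3 cm² (0.25 mg/cm²); 0.05 ml per drop; 5 ml per bottle. From the Protocol Summary: daily application for 12 weeks (12 × 7 = 84 days) and eligible area 0.5 to 20 cm².

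**Reproducing the table.** Volume = drops × 0.05 × 84, and bottles = volume / 5 rounded up.

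- 1 drop: 4.2 ml, 1 bottle
- 2 drops: 8.4 ml, 2 bottles
- 3 drops: 3 × 0.05 × 84 = 12.6 ml, 3 bottles

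Every row reproduces, so the table is consistent with itself.

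**Table against the stated rate.** The rate is used literally, since no rounding rule is given.

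| Area (cm²) | Rate: drops; mg/day | Table: drops; mg/day | Table / rate |
|---|---|---|---|
| 5 | 5; 1.25 | 3; 0.75 | 3/5 = 60% |
| 10 | 10; 2.5 | 3; 0.75 | 3/10 = 30% |
| 20 | 20; 5.0 | 3; 0.75 | 3/20 = 15% |

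At 20 cm² the two readings differ by 5.0 / 0.75 = 6.7-fold. The open-ended row spans (20 − 3)/(20 − 0.5) = 17/19.5 = 87% of the eligible range. That is a share of the range, not of patients, because the plan gives no size distribution. In the lower rows the gap stays below one drop a day (0.6 v 1 at 0.6 cm², 1.9 v 1 at 1.9 cm², 2.9 v 2 at 2.9 cm²).

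**Bottles.** Two bottles hold 10 ml. At the table's 0.15 ml/day, 10 / 0.15 = 66.7, so 66 full days, 18 short of 84. Three bottles (15 ml) do cover 12.6 ml. This conflict does not depend on how the per-area rate is read.

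**Conditional run-out.** This applies only if drops follow the sentence while bottles follow the table (15 ml).

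- Constant area A: days = 15 / (0.05A), which gives 60 at 5 cm², 30 at 10 and 15 at 20. Total need is 4.2A ml, so run-out begins above 15/4.2 = 3.6 cm².
- Area shrinking linearly to zero at day 84, with drops reduced in step: solve 0.05A(t − t²/168) = 15. This gives t = 39.1 at 10 cm² and 16.7 at 20 cm² (39 and 16 full days). Total need is 2.1A ml. At 5 cm² that is 10.5 ml and the supply lasts; run-out begins above 15/2.1 = 7.1 cm².

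**Band gaps.** Read literally to one decimal, 0.5, 1.0, 2.0 and 3.0 cm² belong to no row. At 0.5 and 1.0 the neighbouring rows agree. At 2.0 they differ (1 v 2 drops and bottles), and at 3.0 they differ (2 v 3). The second of these is the reference area of the dose sentence itself.

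**Smaller points.** The plan does not say whether drops are fixed at randomisation or follow the weekly measured area. The < 0.5 row lies below the entry minimum and makes sense only if drops follow a shrinking ulcer. The ocular reference, "the recommended ocular dosage is 0.25mg/day (1 drop in each eye once a day", leaves open whether 0.25 mg is per eye or in total; the table uses 0.25 mg per drop.

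**The case against.** The best defence is that the table is the operating rule. The sentence before it defers to it, each row gives a complete and consistent prescription, and the top row can be read as a deliberate cap. On that reading the per-area sentence is only a headline, and the run-out figures mix cells that belong together. That reading is possible, but no passage states it. The 0.7 ng/ml serum rule in Section 4.3.3 ends participation for a patient and does not limit the dose. Even with a cap, the two per-area sentences would be wrong for larger ulcers and the bottle phrase would still be wrong. The run-out figures are properly conditional and the conclusion does not need them.

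Drops are whole, and the lower rows appear to round down. With that rounding, sentence and table agree up to 3.9 cm² and diverge from 4.0 cm², where 4 drops need 4 × 0.05 × 84 = 16.8 ml against 15 ml. This is fair, but it moves only where the conflict starts.

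The bottle phrase may be a drafting slip, and treatment stops at healing, so not everyone needs 84 days. Yet Section 6 expects 20% of control and 63% of timolol patients to heal by week 12. That leaves 80% and 37% unhealed and, if still on treatment, needing the full supply.

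Reading > as ≥ would close the gaps at one decimal, though an area such as 1.95 or 2.95 cm² would still have no row.

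Finally, the primary Fisher test compares closure by arm and does not use dose. That stands: the randomised comparison is not biased by this.

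**Conclusion.** The concern holds: the dose instruction is wrong as written, and the dose sentences, table and bottle count cannot all be followed for larger ulcers. The table gives 60%, 30% and 15% of the stated rate at 5, 10 and 20 cm², assuming the rate is applied literally. With whole drops rounded down, the conflict starts at 4.0 cm² instead of just above 3.0. The bottle contradiction (two bottles last 66 of 84 days) needs no assumption beyond the table's own figures and full-length treatment.

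The comparison between arms stays valid. What is lost is a single definition of the regimen for larger ulcers, with up to a 6.7-fold difference in total daily dose. How many patients this touches is unknown. Because it concerns the definition of the investigational treatment and bears on safety, it must be fixed.

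**What to change.** After clinical and pharmacy review, bring the two dose sentences, the table, the bottle count and the 0.5 to 20 cm² eligibility range into one rule. The revised text should:

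- say in words whether the table's top row is a cap;
- assign every eligible area to exactly one row, including exactly 2.0 and 3.0 cm²;
- say whether the number of drops is fixed at randomisation or follows the measured area;
- confirm that the bottles dispensed cover 84 days under that rule;
- clarify the ocular reference wording.

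This review takes no view on which dose is right. The cost is protocol wording and the review behind it, with no new data and no change to the analysis.
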